(3) Is the *improvised dressing* culturally acceptable to health care providers, patients, and families for managing SCLUs in Jamaica?

The expected study outcome is improvised dressing superior effectiveness and quality of life, when compared with usual practice, without increased safety and acceptability issues.^{13,59,60,62} The improvised dressing is likely to be the least expensive choice, with the added benefit of being available as first aid treatment throughout Jamaica. The advanced dressing is likely to be more expensive with respect to materials costs, although fewer dressing changes are anticipated and pain medication expenses are likely to be reduced. Based upon the review of the literature, no serious infections or other safety issues are anticipated for any group. However, to ensure that complications are not overlooked, in addition to the onsite researchers' vigilance, weekly wound photos will be assessed for complications (signs of infection, wound deterioration, or clinically relevant maceration) by two off-site blinded wound experts, Drs. [name] and [name].

Definitions:

Sickle cell leg ulcer – a wound in a HbSS or HbS β^0 positive patient, open greater than one month,⁷ below the level of the knee excluding the plantar surface of the foot.

Closed wound -100% epithelialized with no discernible scab or exudate production (paper napkin remains dry when lightly pressed against area, and no recurrence in the subsequent two weeks)

Safe – infection and other complications (healing-impairing maceration, keloid, and contracture rates) not statistically significantly higher than usual practice, with no major adverse events attributable to the method

Effective – ulcer closure rates or ulcer surface area reduction rates not statistically significantly lower than usual practice

Acceptable – average acceptability scores of 4 or higher on a 1-5 scale

3. Methods and Materials

a. Study design

This study will be a targeted-blinded (the off-site wound experts and the local physicians verifying wound closure and/or complications will be blinded to the randomization group), randomized controlled trial with three arms: (1) usual practice (negative control), (2) the improvised dressing, and (3) the advanced dressing (positive control). The expected outcome is improvised and advanced dressing superiority.

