Weekly, de-identified photographs will be sent by the Principal Investigator to be viewed by two blinded wound experts ([name] and [name]) off site. If the blinded experts, or anyone else involved in the study, expresses concern that a patient is exhibiting signs of possible infection, maceration that is delaying healing, or wound deterioration, a physician at UHWI or the SCU who is not otherwise involved in the study will be asked to evaluate that patient. The patient's dressings will be removed prior to this evaluation so that their treatment group will not be revealed to the physician (the evaluation by the physician is thus blinded to treatment group). If the physician determines that the patient's condition has not improved with the prescribed treatments (e.g., antibiotics), the patient will be withdrawn from the study. Any

patient who transitions out of the group to which they were randomized for any reason will receive usual treatment for their ulcer for the remainder of their 12 week study period.

When the treatment personnel at UHWI or the blinded remote observers state that the patient's wound appears to be closed, a physician at UHWI or the SCU who is not otherwise involved in the study will be asked to evaluate that patient. The patient's dressings will be removed prior to this evaluation so that their treatment group will not be revealed to the physician. Wound closure is defined as 100% epithelialized with no discernible scab or exudate production (a paper napkin blotting the area remains dry). Patients will be reassessed two weeks later to verify that the wound was truly closed and did not immediately recur.

Patients who are diagnosed with wound closure or have completed the 12 week study period will be taken aside privately and asked to rate the acceptability of their treatment using a 5 point Likert Scale. A family decision-maker will also be privately asked to rate the acceptability of the treatment. One of the research team members will enter this basic acceptability data for the patient and the family on the patient's Data Collection Tool. At that point, the patient will graduate from the study. However, patients and families will be instructed to return to UHWI for follow-up if a complication or recurrence develops. Any delayed complications (e.g., recurrence within 3 months) will be recorded on the patient's Data Collection Tool by the nurse or physician to whom the patient reports it.

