Research questions (1) and (2) will be addressed by using analyses of covariance (ANCOVA) to determine if patients in the improvised dressing group (Group 2) had superior results (95% CI's will fall within *f*, the superiority margins) from usual practice (Group 1) or advanced dressings (Group 3), or, if this is not demonstrated, failed to vary significantly (80% CI's will fall within *f*, the inferiority margins) from usual practice (group 1) or advanced dressings (group 3) with respect to each of the dependent variables, controlling for relevant patient characteristics (the independent variables).

Research question (3) will be addressed with descriptive statistics across Likert items regarding endorsement of and concerns with use of the improvised dressing clinically or in future studies. Qualitative comments will be summarized across providers into content themes. Any differences between nurses, patients, family members, and physicians will also be explored and noted.

All health care providers at UHWI participating in the study will be surveyed to explore their concerns as well as their opinions about each dressing choice, using both qualitative open-ended and a quantitative question on a Likert scale. Results will then be shared with the participating clinical staff to provide them with the evidence concerning each of the three dressing protocols.

j. Data handling and record keeping

All study data will be transferred from written documents to the Principal Investigator's password protected electronic devices, de-identified, and then transmitted over secure internet connections to the backup hard drive in the USA. The paper study documentation and the two encrypted USB drives containing the raw data will be stored in a securely locked file in in [name] office in UWI Department of Surgery for a period of at least two years after the study has been published, after which they may be destroyed.

When all of the patients have completed the study, members of the UHWI research team will proofread the Excel spreadsheet with the de-identified data for transcription errors. This data will then be evaluated by the biostatistician using the most recent version of SPSS.

4. Ethical Considerations

This study will be approved by the Ethics Review Committee (ERC) at UWI and the Jamaican Ministry of Health (MOH) prior to its implementation. It will be listed on clinicaltrials.gov prior to the recruitment of the first study patient.

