SCLUs are often disabling, scarring, and exquisitely painful. The research literature suggests that both the improvised dressing and the advanced dressing can decrease pain. The advanced dressing has also been shown to decrease scarring. However, children ages 13 - 18 are an especially vulnerable population. They are included in the study because this is the peak age group for SCLU formation, and therefore they are the most likely to benefit if the results can be generalized to them.¹⁵

5. Limitations

Blinding is a challenge inherent to studies of wounds. Although the the healthcare professionals who will monitor and verify wound closure and complications (outcomes) will be blinded, it is not possible to blind the participants or the research team members, because they will provide the wound management in this study.

Despite the incentives to remain in the study (phone cards monthly and wound management supplies at the conclusion of the study), it is possible that there will be a substantial dropout rate, because it is easy for patients with SCLUs to become discouraged, and they may feel that they have derived the major benefits of joining the study after the first few weeks.

All of the published studies of improvised dressings describe wound care performed by health professionals based in urban hospitals or long term care facilities. Although this study will be conducted in a tropical outpatient setting, it too is being conducted by health care professionals in an urban area. Also, Jamaica is significantly more developed than many of the countries for whom the improvised dressing educational program may be beneficial. Therefore, this study may not uniformly generalize to rural areas of tropical developing countries, where health professionals are absent.

6. Acknowledgments:

The researchers would like to thank all participants in the study.

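### Patient and family acceptability ratings pass through the unblinded treating team and are judged against a fixed mean of 4; a sealed, self-marked card would be a cheap improvement

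*Combined protocol and SAP*

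**What the plan says.** Research question 3 asks whether the improvised dressing is culturally acceptable to providers, patients and families. The definitions in section 2 of the combined protocol and SAP set the criterion: "average acceptability scores of 4 or higher on a 1-5 scale". They name no comparison arm and no confidence bound. Section 3i adds that the question "will be addressed with descriptive statistics across Likert items regarding endorsement of and concerns with use of the improvised dressing".

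Section 3h describes how the ratings are collected. Patients whose wound has closed, or who have completed 12 weeks, are "taken aside privately and asked to rate the acceptability of their treatment using a 5 point Likert Scale". For relatives: "A family decision-maker will also be privately asked to rate the acceptability of the treatment". Then: "One of the research team members will enter this basic acceptability data for the patient and the family", on the patient's Data Collection Tool. De-identification is a later step, done by the Principal Investigator.

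Section 5 states that "it is not possible to blind the participants or the research team members, because they will provide the wound management in this study". The blinding in section 3a covers other outcomes: "the off-site wound experts and the local physicians verifying wound closure and/or complications will be blinded to the randomization group".

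Two further provisions matter. Section 3i plans to compare the groups on all 14 dependent variables, and section 3d lists patient, family and staff acceptability as items 12 to 14. Section 3i also provides a separate survey of the participating health care providers.

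**The concern.** People tend to rate a treatment more kindly when those who gave it will see the answer. Here the answer goes onto a form that identifies the patient and is written there by a member of the team that manages the wounds. The same team gives phone cards as thanks, and dressings and wound care are free. Asking in private shields the patient from the family, and the family from the patient. It does not separate either of them from the team.

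For closure and complications, section 3h brings in a physician not otherwise involved in the study. Acceptability has no comparable separation.

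The form of the criterion adds to this. A difference between arms would be largely protected against a courtesy shift shared by all arms. A fixed cut-off is not: every tenth of a point of courtesy moves the observed mean a tenth of a point towards 4. Acceptability is one of the trial's three research questions. Section 1b says earlier moist dressings tried locally fell short on results, on patient acceptance, or on both, so whether patients really accept this one is an open question.

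**Working it through.** **Inputs from the documents.** The criterion is an observed mean of at least 4 (section 2). Section 3f gives 90 participants, about 30 per group, with up to 120 recruited to allow for 25% dropout. This reproduces: 90 / (1 − 0.25) = 120, or 40 recruited and 30 remaining per arm. The plan gives no expected mean, SD or size of courtesy effect for the acceptability item.

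**Assumptions.** SD of 1 (range 0.8 to 1.2), 30 raters, true mean *m*, and courtesy shift *b*.

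**Formula.** P(observed mean ≥ 4) = 1 − Φ((4 − m − b) / (SD/√n)). With SD 1 and n = 30, the standard error is 1/√30 = 0.183.

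**Worked case.** For m = 3.8 and b = 0, z = 0.2/0.183 = 1.10, so P = 14%. With b = 0.2, z = 0 and P = 50%. With b = 0.4, z = −1.10 and P = 86%.

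| True mean | no shift | +0.2 | +0.3 | +0.4 |
|---|---|---|---|---|
| 3.8 | 14% | 50% | 71% | 86% |
| 3.5 | 0.3% | 5% | 14% | 29% |

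**Range over SD 0.8 to 1.2.** A true mean of 3.75 passes 4–13% of the time with no shift, 50% with +0.25 and 87–96% with +0.5. A true mean of 3.0 passes at most 1.1% with +0.5, and needs +1.0 to reach 50%.

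**Check on a real 5-point scale.** Simulated ratings, with a share of raters adding one point and scores capped at 5, show the same pattern:
- Mean 3.8: passing rises from 15% to 86% if half the raters add a point.
- Mean 3.5: it rises from 0.6% to 35% if half do, and to 76% if three quarters do.
- Mean 3.0: it reaches only about 32% even if everyone does.

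**Fixed threshold against between-arm contrast.** With the same shift *b* in both arms, the difference is (m₂ + b) − (m₁ + b) = m₂ − m₁, so *b* drops out. Against the threshold, m₂ + b − 4 still contains *b*. The planned comparison therefore gives some protection, but it is weak at this size. With 30 per arm, power to detect a difference of 0.5 points (two-sided 5%) is 68%, 49% and 36% for SDs of 0.8, 1.0 and 1.2. The definition of acceptability does not use that comparison.

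**The case against.** The strongest reply has four parts.

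- **The text does not say the rating is spoken to a caregiver.** Section 3h is in the passive. It names no asker and no mode, and entry by a team member fits transcription from a form as well as an oral answer. This stands: the defect is that asker and mode are unspecified. It does not remove the concern, because a team member handles the rating either way and no self-completed or anonymous form is described.
- **Much of the care is self-care.** Patients change their own dressings at home, and after week 4 some may report remotely. They are partly rating something they apply themselves. This weakens the pull of courtesy, but section 5 still says the team provides the wound management.
- **Other evidence bears on question 3.** Staff have their own survey, raters give free responses, differences between rater types are explored, and the arms are compared on acceptability. A reader might infer that patient politeness alone settles the acceptability verdict. The documents do not support that. They give no rule for combining rater groups, and if each group must reach 4, inflated patient scores could not carry the verdict.
- **The numbers are hypothetical and favour a mean near the cut-off.** This is true. At a true mean of 3.5, even the +0.4 shift leaves a 71% chance of failing.

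**Conclusion.** The point holds as a cheap improvement, not as a flaw that undermines the trial. The method described leaves patient and family ratings open to courtesy inflation, and the fixed mean of 4 lets such inflation pass straight into the verdict.

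The effect matters when true acceptability lies a little below 4. At a true mean of 3.8, a shift of 0.2 takes the chance of passing from about one in seven to one in two. At 3.5 the largest shift tabulated gives less than one in three, and near 3 only about a full point would do. A reader might infer that any poorly accepted dressing could be carried over the line; the figures do not show that. All of them rest on an assumed true mean, SD and shift, because the plan supplies none.

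Nothing here concerns the staff survey. A shared shift would also cancel, at least approximately, in the planned between-group comparison.

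**What to change.** In section 3h, replace the asked-and-entered rating with a self-marked one. The patient and the relative each mark the 5-point item and write the free response alone, on a card bearing only the study number, and seal it in an envelope. The envelope is opened and entered later by an existing team member who did not dress that patient's wounds.

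The cost is a printed card and an envelope per rater and a short change of text. No extra staff are needed, and visits, sample size, the threshold and treatment stay as they are. The downside is that a few raters will need the item read aloud. An available team member can do this, and it should be noted on the card so that those ratings can be identified. The card reduces the pressure to please without removing gratitude altogether. It is still worth having, because later analysis cannot take a shift of unknown size out of the recorded scores.

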Decrease in SCLU surface area will be used to answer research question 1. Conducting a power analysis for this study is challenging because only one study of SCLUs has demonstrated a statistically significant outcome, and the effect size was obscured by high standard deviations, which is a common problem in studies of wounds.⁸ Improvised plastic dressings similar to the study dressings were used in 49 chronic pressure ulcers in elderly patients, which are often slow to close, if they heal at all.⁶⁰ These two studies demonstrated a significant difference with confidence intervals of 99% with ~25 patients per group. Based upon these sample sizes and the Central Limit Theorem, it is reasonable to set the minimum sample size for this study at 30 patients per group,.^{88,89}

d. Variables

Dependent Variables (measured weekly - tools and permissions in appendices):

- 1. Persistent wound pain (using the Faces Pain Scale Revised (FPS-R))
- 2. Procedural (dressing change) wound pain
- 3. Amount of pain medication taken, including a total number of morphine equivalents plus non-opioid pain medications
- 4. Approximate time spent standing, or sitting with leg dependent without compression (estimated hours per week)
- 5. Patient overall quality of life (assessed with the ASCQ-Me Emotional, Pain, Social Functioning, Stiffness, and Sleep Impact Short Forms)
- 6. Patient wound-specific quality of life (assessed with the Wound QoL tool)
- 7. Materials costs (estimated, using lowest retail costs on Amazon.com for items not on the UWI price sheets)
- 8. Time spent performing dressing changes
- 9. Wound complication rates (e.g., wound infection, healing impairing maceration, wound deterioration)
- 10. Change in wound surface area (measured in cm² electronically using software that automatically corrects for skew, such as HealthEPix or WoundMatrix)⁹⁰

Dependent Variables (measured one time, at graduation from study)

- 11. Wound closure time, in weeks (see definitions; verified two weeks later. Omit patients whose wounds did not fully close they are included in 10., above.)
- 12. Acceptability of dressing choice patient (5 point Likert scale and qualitative free response)
- 13. Acceptability of dressing choice family member (5 point Likert scale and qualitative free response)
- 14. Acceptability of dressing choice UHWI staff (5 point Likert scale and qualitative free response)

Independent Variables (documented at initial study visit):

1. Patient gender

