As a token of appreciation from the research team and an incentive for patients to return for their study clinic visits, each participant will be presented with a 500JM phone card at the end of each of the three 4-week study periods.

All wound management supplies for all three groups will be donated. Shipping and handling fees will be paid by the Principal Investigator with funds from a Wound Healing Foundation grant. Tallies of supplies used at dressing changes will be priced using the cost of medical supplies purchased by the SCU to determine the estimated cost of the treatment supplies for each patient. The PMD rolls will be valued at \$26.99US.⁹⁸

The Principal Investigator will de-identify the data and compile it from the patient Data Collection Tools onto an Excel spreadsheet. This spreadsheet and the de-identified wound photographs will be backed up onto the Principal Investigator's second password protected hard drive via a secure internet connection at least weekly. Two encrypted USB drives containing the data, including wound photographs, will be updated weekly on an alternating schedule and stored in a securely locked file in [name] office in UWI Department of Surgery.

i. Statistical analysis

A consultant, [name], PhD, Senior Biostatistician at The University of Texas Medical Branch in Galveston, will undertake the analysis.

When all of the patients have completed the study, the remainder of the data from the deidentified Data Collection Tools will be transcribed into an Excel spreadsheet by the Principal Investigator. The data will then be evaluated by the biostatistician using the most recent version of SPSS. Groups will be compared with respect to each of the 14 dependent variables, taking into account any confounding from the 11 independent variables. Results will be reported using descriptive statistics (means, modes, medians, frequencies), student's t test, and ANOVA with 95% CIs, using intent-to-treat.¹³ If the improvised dressing does not attain statistical superiority to usual practice, 80% CIs will be calculated with drop-outs removed from the analyses to evaluate noninferiority.^{13, Appendix: From Oczkowski SJW} Complications will be evaluated both individually and collectively by collapsing the pertinent columns.

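### Complication rates decide the safety verdict but are assigned to the t test, ANOVA and ANCOVA, which fail with no events and, for ANOVA and ANCOVA, mislead with few

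*Combined protocol and SAP*

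**What the plan says.** The definitions in section 2 make safety a significance statement: "infection and other complications (healing-impairing maceration, keloid, and contracture rates) not statistically significantly higher than usual practice", together with no major adverse events attributable to the method. Section 3d lists the outcome as dependent variable 9, among those measured weekly: "Wound complication rates (e.g., wound infection, healing impairing maceration, wound deterioration".

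Section 3i, Statistical analysis, then sets the methods.

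- Scope: "Groups will be compared with respect to each of the 14 dependent variables".
- Tests: apart from descriptive statistics, "student's t test, and ANOVA with 95% CIs, using intent-to-treat".
- Model: "Research questions (1) and (2) will be addressed by using analyses of covariance (ANCOVA"). Research question 1 is the one that asks about safety. The model is applied "with respect to each of the dependent variables, controlling for relevant patient characteristics", of which 11 are listed.
- If superiority is not shown, 80% intervals with drop-outs removed are compared with an inferiority margin called *f*. The supplied text gives *f* no value.

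One sentence in 3i is specific to complications. It says they will be looked at singly and pooled, and names no test. Frequencies appear only as descriptive statistics. The text names no chi-square or exact test, no interval for a proportion and no logistic model. On expected results, section 2 says "no serious infections or other safety issues are anticipated for any group".

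**The concern.** Having a complication is a yes/no outcome, and some types will be rare. The methods named in 3i compare means and estimate a variance from the data. That variance is zero when nobody has an event. When only one arm has events, the variance pooled over three arms is too small for that arm. Both situations are plausible at about 30 patients per arm.

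The verdict on this variable carries weight. Section 1b gives the risk of wound infection in a tropical climate as the reason to test the dressing under professional guidance first, and a favourable result is meant to support self-care. An interval of exactly 0 to 0 would hide how little 30 patients can exclude. In the other direction, three events could make the dressing look significantly worse because of the variance model and not the data.

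**Working it through.** **Inputs.** About 30 patients per group and 90 in all, 25% dropout, a ceiling of 120 (section 3f); 95% and 80% intervals (3i). The plan gives no complication rate and the supplied text gives no margin, so the risks and the 10-point margin below are assumptions.

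**The plan's own figure.** 90 / (1 − 0.25) = 120, or 40 per arm. This reproduces. The 30 per group cannot be derived, because no effect size, SD, event rate or power is stated.

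**No events.** If neither compared arm has an event, the two-sample variance is 0. The interval is 0 ± t × 0 = 0 to 0 at any confidence level, and the t statistic is 0/0. If all three arms have none, the ANOVA F is 0/0 and ANCOVA cannot be fitted. For comparison, the Wilson upper limit for 0/n is z²/(n + z²):

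- n = 30: 3.84 / 33.84 = 0.114. Newcombe 95% interval for 0/30 v 0/30: −11.4 to +11.4 points (80%: ±5.2).
- n = 40: 3.84 / 43.84 = 0.088. Newcombe 95% interval: −8.8 to +8.8 points (80%: ±3.9).

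The chance of no events in two arms of 30 is 0.99^60 = 55% if each patient's risk is 1%, and 0.98^60 = 30% if it is 2%.

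**Three events in the improvised arm, none in the other two, 30 per arm.** The means are 0.1, 0 and 0.

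- Within-group sum of squares: 3 × 0.9² + 27 × 0.1² = 2.7. Between-group: 30 × (0.0667² + 2 × 0.0333²) = 0.2.
- ANOVA: F = (0.2/2) / (2.7/87) = 3.22 on 2 and 87 df, p = 0.045. Exact three-arm test (Fisher-Freeman-Halton): p = 0.104.
- Contrast with usual practice using the pooled variance: t = 0.1 / √(0.0310 × 2/30) = 2.20 on 87 df, p = 0.031.
- Two-sample t test: variance 2.7/58 = 0.0466, t = 1.80 on 58 df, p = 0.078.
- Two-arm exact tests: Barnard p = 0.092, Fisher p = 0.24.

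The third arm adds 29 degrees of freedom and no variation, which is what moves p from 0.078 to 0.031. At 40 per arm the ANOVA p is 0.046 and the contrast p is 0.031. Simulated ANCOVA with 11 assumed normal covariates unrelated to outcome gave a median contrast p of 0.043 at 30 per arm.

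**Other sparse tables, two arms of 30.** The unconditional tests take the maximum over the common risk on a fine grid.

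| Events | t test p | Barnard p | Boschloo p | Fisher p | Newcombe 95% (points) |
|---|---|---|---|---|---|
| 3 v 0 | 0.078 | 0.092 | 0.155 | 0.237 | −3.1 to 25.6 |
| 4 v 0 | 0.039 | 0.047 | 0.070 | 0.112 | −0.6 to 29.7 |
| 5 v 0 | 0.019 | 0.023 | 0.027 | 0.052 | 2.0 to 33.6 |
| 6 v 1 | 0.045 | 0.055 | 0.056 | 0.103 | −0.3 to 34.2 |

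**Size of the two-sample t test at nominal 5%, 30 per arm, by full enumeration.** 0.3% at a 2% risk, 2.8% at 5%, 5.4% at 10%. Fisher at the same risks: below 0.01%, 0.2%, 0.9%.

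**80% interval for non-inferiority.** Full enumeration at 30 per arm, with the true excess equal to an assumed 10-point margin. The nominal false pass rate is 10%.

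| True risks | t-based passes | Newcombe passes |
|---|---|---|
| 0% v 10% | 18.4% | 4.2% |
| 2% v 12% | 13.2% | 8.4% |
| 5% v 15% | 10.8% | 10.0% |
| 10% v 20% | 10.3% | 10.3% |

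**The case against.** Several stronger readings are tempting, and the documents do not support them.

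- *The plan expects no complications at all.* Section 2 rules out only serious infections and other safety issues. Variable 9 also covers lesser infection, maceration and deterioration. Section 1a says these ulcers often enlarge in the first four weeks and cites three cases of maceration in an earlier plastic-wrap study. Zero is plausible for single rare types, not for the pooled outcome.
- *A 0 to 0 interval would be passed off as proof of safety.* The safety definition uses no margin. At 0 v 0 Fisher gives p = 1 and the same label, and software would show the planned test as undefined. The label stands; only the missing uncertainty is at fault.
- *The t test produces false alarms.* It does not at low risk, its size only slightly exceeds 5% near a 10% risk, and it lies close to Barnard. Comparing it with Fisher alone exaggerates the gap, because Fisher is very conservative here.
- *One infection will be counted several times.* The variable is recorded weekly and no unit of analysis is stated, so this could happen. Nothing says that weekly rows will be treated as independent.
- *Fisher's test is the remedy.* Under this definition a non-significant result means safe, so a conservative test makes harm easier to miss. At 5 v 0 Fisher gives 0.052 while the Newcombe interval excludes zero.

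The non-inferiority appendix cited in 3i was not available and may give *f* a value. What stands is the mismatch between the outcome and the named methods, the uninformative result with no events, and the pooled-variance fault in ANOVA and ANCOVA.

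**Conclusion.** The point holds in limited form and should be fixed. Section 3i prescribes comparisons of means for the variable that decides safety and names nothing suited to proportions. With no events the planned output cannot show that an excess of about 11 points (about 9 at 40 per arm) remains possible. With few events in one arm, ANOVA and ANCOVA can cross 0.05 on three events where neither the t test nor an exact two-arm test does. The 80% interval is too lenient at a base risk of 0% to 2% and near nominal at 5% to 10%. That last result depends on an assumed 10-point margin. The ANCOVA figure depends on assumed covariates.

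This is not a claim of general type I error inflation, and the label at 0 v 0 would not change. What changes is the stated uncertainty, and the verdict when events are few.

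**What to change.** In 3i, take variable 9 out of the t test, ANOVA and ANCOVA list. Analyse the proportion of patients with at least one confirmed complication, each patient counted once, overall and by type. Report the risk difference between improvised dressing and usual practice with a Newcombe or Miettinen-Nurminen 95% interval.

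Take the decision on whether the rate is significantly higher from that interval, or from a matching unconditional exact test (Barnard or Boschloo), and not from Fisher. Name the deciding method in advance, because close cases differ: at 4 v 0 Newcombe includes zero and Boschloo gives 0.070, while Barnard gives 0.047. Newcombe and Boschloo agree in all four tables shown above.

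Print the upper limit beside any statement that the dressing is safe, so that no events is not read as proof of no excess.

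The change is to the wording of the analysis section and needs no new patients, visits or data. The price is a wider and less favourable safety interval.
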